 CR  RP	[name], MSc Type Here	 Faculty  Staff  Grad Student  Undergrad  Other UCI: Type Here	 N/A  Yes  No	 N/A  Yes  No	 N/A  Yes  No	 N/A  Yes  No	 N/A  Yes  No
 CR  RP	[name] Postdoc	 Faculty  Staff  Grad Student  Undergrad  Other UCI: Postdoc	 N/A  Yes  No	 N/A  Yes  No	 N/A  Yes  No	 N/A  Yes  No	 N/A  Yes  No
To add more study team members, click into this space, then click the new + button on the right 							

5. If applicable, specify which members of the above study team will be responsible for interacting with non-English speaking participants.
 
NA: English speaking participants only
							

SECTION 3: WHAT IS YOUR RESEARCH QUESTION?

1. State the hypothesis or primary objective of the research. Include a rationale for conducting the study. *[Maximum length = 250 WORDS]*

This study seeks to utilize our previously tested Harnessing Online Peer Education (HOPE) online community intervention to connect peer leaders with healthcare personnel and frontline essential workers choosing not to receive the COVID-19 vaccine. Over the 4-week intervention we aim to teach participants about the risks of COVID-19 and the benefits of the COVID-19 vaccine.

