The peer community leader model, which teaches community popular opinion leaders about how to disseminate behavior change messages throughout the community, has been proven to increase prevention behaviors in things like HIV prevention. Social networks, such as Facebook.com may be a cost-effective platform for scaling these models. Our research team has employed our HOPE intervention previously, for example, in populations who are high risk for HIV/AIDS and in populations suffering from anxiety due to COVID-19. Following that same model, we will modify it to help combat the current low rates of COVID-19 vaccination, with some places experiencing as high as 50% of healthcare personnel refusing to receive the COVID-19 vaccine. If we are able to increase the rates of COVID-19 vaccination, it will show potential as a useful tool to aid in future public health crises and vaccination campaigns.

2. COVID-19: Does this research include a focus on SARS-CoV-2/COVID-19 (Coronavirus)?

NO

YES: Please consider whether [Ancillary Committees for COVID-19 Research](#) apply.

SECTION 4: SUBJECT POPULATION

Complete the table below. Specify the maximum number of individual-level information to be accessed/analyzed within each cohort and in total across all cohorts.

Category/Group (e.g., students in School or Course, consumers on website, people being observed at location)	Age Range (e.g., adults 18 and over)	Maximum Number of Subjects
American Adult in phase 1a or 1b of COVID-19 vaccine rollout who have refused to receive the COVID-19 vaccine	18+ years old	120
Type Here	Type Here	Type Here
To add more categories/groups, click into this space, then click the new + button on the right 		
		Total: 120

SECTION 5: RECRUITMENT METHODS

1. Indicate which recruitment methods will be utilized. Check all that apply:

IMPORTANT! Advertisements must adhere to UCI [Recruitment Guidelines](#). Various templates are available on the HRP webpage [Application and Forms](#) (see sub-section HRP and then Recruitment Templates).

This study involves no direct contact with participants (i.e., passive observation of public behavior or secondary use of information). **Skip to SECTION 6.**

Online Advertisements – Including Social Media Radio / Television Advertisement

Newspaper Advertisement Flyers

Letters or Emails Phone Call

Other (specify): [Type Here](#)

2. Describe when, where, by whom and how potential participants will be approached.

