3. If posting on your Facebook page or other social media sites, please explain.

4. If you will recruit by e-mail, phone, etc., explain how the researcher will obtain the participants' contact information.

Participants in both the control and intervention group will be recruited through online advertisements on Facebook, Google ads, our Facebook page, and online forums like Reddit. We may also contact healthcare organizations, hospital departments, and academic institutions by phone or email asking them to send emails with information about the study to any frontline essential workers through a mailing list.

Advertisements will be designed to recruit healthcare personnel and frontline essential workers who have refused to receive the COVID-19 vaccine. Participants who click on the ads or links on the forums will be routed to a website/survey (such as Qualtrics) where they are screened online for eligibility with our questionnaire. Those who visit our Facebook page may have the option to interact with a chat box that will eventually route potential participants to the website/survey as above.

Inclusion criteria:

1. Adults, 18+ years old, who are competent to give informed consent
2. English speakers only
3. U.S. Resident
4. Part of phase 1a or 1b of COVID-19 vaccine rollout – healthcare personnel and frontline essential workers (employment verified through LinkedIn profile or similar)
5. Uses social media and/or online communities greater than twice per week
6. Has, or is willing to accept a friend request and group invite from our Facebook social media page
7. Has not received a COVID-19 vaccine and does not have medical conditions or other circumstances preventing them from receiving one

Phase 1a includes **healthcare personnel** such as physicians, nurses, technicians, therapists, pharmacists, administrative staff, environmental services staff, students, and other trainees.

Phase 1b includes **frontline essential workers** such as fire fighters, police officers, corrections officers, food and agricultural workers, United States Postal Service workers, manufacturing workers, grocery store workers, public transit workers, and those who work in the educational sector (teachers, support staff, and daycare workers.)

See CDC recommendations for further details: <https://www.cdc.gov/coronavirus/2019-ncov/vaccines/recommendations.html>

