Those who do not qualify to participate in the study will see a web page that thanks them for their interest and tells them that they are not qualified to participate at this time and that their data will not be used and will be destroyed to protect their confidentiality. Those who are unqualified will not be able to access the Informed Consent Information Sheet. If eligible, potential participants will be sent a brief description of the study and the Informed Consent Information Sheet. If they would like to participate in the study they will be asked to continue with the consent process. By clicking continue, they will have implied consent to the study and be routed to a webpage where they can provide an email address and phone number for future contact, as well as begin the baseline survey. After survey completion, they will be instructed to friend request our HOPE Study Facebook profile or be provided a link to join the group.

After 1) consenting to the study (by clicking continue), 2) friending us on Facebook, 3) completing a baseline survey, and 4) joining our private Facebook group (they will be randomly assigned to a group and group request will be sent to them), participants will be officially enrolled in the study.

If participants have yet to friend us or join our private group, we will email them a reminder and/or call them every 24 hours until the invitation is accepted.

In the event that a participant has trouble friending us on Facebook, participants may alternatively be sent a link to join the Facebook group.

If the baseline survey is not completed after 48 hours, we will attempt to reach the participant by phone every day until we successfully make contact. We may call them multiple times per day up to a maximum of 3 attempts.

Peer Leader Recruitment:

Up to 30 peer leaders will be recruited using online advertisements as above, as well as by direct message of healthcare personnel or frontline essential worker that has shared a picture of their vaccine card or vaccination sticker online, for example on Reddit. Advertisements will be designed to recruit people who are social online (e.g., chat frequently online, create TikTok videos, etc.) and report having received the COVID-19 vaccine. Potential peer leaders who click on the ads will be routed to a website/survey (such as Qualtrics) where they are screened online for eligibility with our questionnaire.

Inclusion criteria:

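### The plan names its population as workers who have refused the vaccine, but no inclusion criterion requires refusal or lack of intention

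*Combined protocol and SAP*

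**What the plan says.** The combined protocol and SAP describes the population three times by refusal or choice. Section 3 (research question) aims the intervention at healthcare personnel and "frontline essential workers choosing not to receive the COVID-19 vaccine". The Section 4 subject table lists American adults in phase 1a or 1b "who have refused to receive the COVID-19 vaccine". Section 5 (recruitment methods) states: "Advertisements will be designed to recruit healthcare personnel and frontline essential workers who have refused to receive the COVID-19 vaccine".

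Section 5 also allows a second route: "We may also contact healthcare organizations, hospital departments, and academic institutions by phone or email", with a request to forward study information "to any frontline essential workers through a mailing list".

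People who follow the advertisements or forum links are "screened online for eligibility with our questionnaire". The questionnaire itself is not reproduced.

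Section 5 then lists seven inclusion criteria. Item 7 is the only one about vaccination: "Has not received a COVID-19 vaccine and does not have medical conditions or other circumstances preventing them from receiving one". There is no separate exclusion list.

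The baseline survey comes before the participant joins the assigned group: "After survey completion, they will be instructed to friend request our HOPE Study Facebook profile".

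Under Methods, the primary outcome is a request for vaccine information and the secondary outcome is vaccination, both during the study. The adjustment covariates are race, age, sex, education and ethnicity.

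**The concern.** A trial of persuasion needs to know whether its participants needed persuading. A worker who has simply not yet gone for the vaccine and a worker who has declined it look the same under item 7, although the plan names only the second as its subject. The first may well be vaccinated within the study in either arm, which leaves the intervention little to change on that outcome.

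Two things are at stake. One is interpretation: a report could present a result as applying to refusers when some unknown part of the sample were not refusers. The other is sensitivity: if planners respond less than refusers, the pooled effect is smaller than the effect the trial set out to estimate. Prior intention is also a plausible strong predictor of vaccination, and it is absent from the stated model. If no instrument records it before the intervention, it cannot be reliably recovered afterwards.

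**Working it through.** **Text check.** There is no sample-size or effect-size figure in the plan to reproduce, so the first step is to set the seven participant criteria against the population statement.

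| Item | Subject | Requires refusal or lack of intention? |
|---|---|---|
| 1 | Adult, competent to consent | No |
| 2 | English | No |
| 3 | U.S. residence | No |
| 4 | Phase 1a/1b occupation | No |
| 5 | Social media use | No |
| 6 | Facebook friend and group acceptance | No |
| 7 | Unvaccinated, nothing preventing vaccination | No: covers status and ability, not willingness |

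The count is 0 of 7. The enrolment steps that follow in Section 5 (consent, friending, baseline survey, joining the group) add no such condition. The plan's own peer-leader rules make a useful contrast. There the advertisement target is people who report being vaccinated, and that target is carried into a criterion (item 7 of the peer-leader list). For participants, the advertisement target is not carried over.

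**Size.** Neither input below is in the documents; both are assumptions.

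- *f*: share of participants who already plan vaccination, the same in both arms in expectation because of randomisation.
- *d*: risk difference in refusers.
- *r*: effect in planners divided by effect in refusers, on the risk-difference scale.

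Pooled risk difference = (1 - f)d + f·r·d = d[1 - f(1 - r)].

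The factor multiplying *d* is:

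| f | r = 0 | r = 0.5 | r = 1 | r = 1.5 |
|---|---|---|---|---|
| 10% | 0.90 | 0.95 | 1.00 | 1.05 |
| 20% | 0.80 | 0.90 | 1.00 | 1.10 |
| 30% | 0.70 | 0.85 | 1.00 | 1.15 |

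For example, with f = 30% and r = 0, 1 - 0.30 × (1 - 0) = 0.70, a 30% reduction. With f = 30% and r = 1.5, 1 - 0.30 × (1 - 1.5) = 1.15, so the pooled result would overstate the effect in refusers by 15%. No event rates are needed for this table. It applies to risk differences, and the proportional change in an odds ratio from a logistic model would differ.

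I do not convert this into a sample size or a head count. A sample-size figure would need outcome rates that the plan does not give, because mixing in planners also changes the outcome variance. A head count would need a settled total, and the plan has two: a maximum of 120 in Section 4, and 5 + 5 groups of about 30 in Methods, which is about 300.

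**The case against.** The best defence is that the gap is narrow. Section 4 is the form's own statement of who the subjects are, and the criteria sit beneath it. A worker in a prioritised group who is unvaccinated and has nothing preventing vaccination is, by elimination, mostly someone choosing not to have it. The wording on other circumstances could even be read to remove a planner who is waiting for supply or an appointment. The advertisements are aimed at refusers. The mailing-list wording says who may receive an email, not who is eligible, and that route is optional. Finally, the screener or the baseline survey may already ask about intention.

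Much of this stands. Item 7 is a partial proxy, the mailing-list route is only weak evidence, and the unseen instruments mean nobody can say from the documents that intention goes unrecorded. But a population description and an advertising target do not test eligibility. Item 7 concerns ability, so a planner with ready access still passes. A screener applies the written rules, and those do not ask for refusal.

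A reader might infer more than this: that planners will in fact be enrolled in numbers, that the comparison is biased, or that the trial will lose a definite amount of power. The documents support none of these. They give no planner share and no event rates, and random assignment means planners should be spread over both arms in expectation.

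**Conclusion.** The mismatch is real and can be checked from the text alone: the population is named by refusal or choice, and eligibility is not. It does not threaten the validity of the comparison between arms. It leaves open whom the result applies to, and it allows possible dilution, mainly of the vaccination outcome. The documents give no specific reason to expect a material effect on information requests.

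Under assumed planner shares of 10% to 30% and relative effects of 0 to 1.5, the risk difference changes by -30% to +15%, with no change if planners and refusers respond equally. Even the direction is therefore unknown. The point is worth correcting because the correction is cheap and the missing information cannot be reliably obtained later.

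**What to change.** **1. Use one definition throughout.** Either:

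- add to item 7, with a matching screener question, that the person has been able to get the vaccine and has declined it or chosen not to get it; or
- keep item 7, and describe the population in Sections 3 and 4, the advertisements and the reports as unvaccinated workers with no barrier to vaccination.

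The first option is worded by past choice rather than current intention so that it agrees with Section 4. A rule based on intention would turn away someone who refused earlier and is now reconsidering, and would admit an undecided person who was never offered the vaccine.

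**2. In either case, measure intention.** Record vaccination intention on a graded scale (for example, definitely not to definitely yes) in the baseline survey, before group assignment. Report its distribution by arm. Pre-specify it as one ordinal or linear adjustment term for both outcomes, with any subgroup result descriptive only. A graded scale is needed because a yes/no item could have little variation left if item 7 is tightened. If the instruments already contain these questions, only the written criteria and the analysis text need to change.

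**Cost.** One survey item, one screener question (only if item 7 is changed), and one extra model term in a small clustered trial. Intention is self-reported and cannot be verified. Recruitment would be somewhat slower if the criterion is tightened.

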1. Adults, 18+ years old, who are competent to give informed consent
2. English speakers only
3. U.S. Resident
4. Part of phase 1a or 1b of COVID-19 vaccine rollout - healthcare personnel and frontline essential workers (employment verified through LinkedIn profile or similar)
5. Uses social media and/or online communities greater than twice per week and is active on TikTok or Instagram (ideally with at least 10,000 followers)
6. Has, or is willing to accept a friend request and group invite from our Facebook social media page
7. Has received a COVID-19 vaccine

Phase 1a includes **healthcare personnel** such as physicians, nurses, technicians, therapists, pharmacists, administrative staff, environmental services staff, students, and other trainees.

Phase 1b includes **frontline essential workers** such as fire fighters, police officers, corrections officers, food and agricultural workers, United States Postal Service workers, manufacturing workers, grocery store workers, public transit workers, and those who work in the educational sector (teachers, support staff, and daycare workers.)

See CDC recommendations for further details: <https://www.cdc.gov/coronavirus/2019-ncov/vaccines/recommendations.html>

As this is a time-sensitive study, peer leaders might be enrolled based on these criteria; however, if time permits, they might also be called and secondarily screened to see whether they are social, communicative, and seem to have leadership qualities based on things like past volunteer experiences. Enrolled peer leaders will be asked to participate in 3 online training sessions of approximately 2-3 hours each where they learn how to interact with participants. Session 1 will focus on COVID-19 epidemiology; session 2 on benefits of the vaccine, as well as fears and myths surrounding the vaccine, and session 3 on the logistics of the study. Peer leaders who complete the training will be paid \$20 per week in Amazon gift cards for emailing us a tracking form by the weekly deadline that documents their efforts attempting to communicate with participants during the course of the study.

Methods:

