Participants will be randomly assigned to an intervention or control group (each group will have approximately 30 participants and approximately 6 peer leaders (depending on recruitment and people that may drop out)). There will be 5 control groups and 5 intervention groups total. Those in the control group will be assigned to a private and hidden Facebook group and told they can interact with each other as they wish. Those in the intervention group will be assigned to peer leaders, also in a private and hidden Facebook group, with each participant assigned to have approximately 2-3 peer leaders. Facebook groups will also become hidden once all group participants are in the group. The intervention will take place over 4 weeks, with a possible week 0 before the study officially starts to allow peer leaders and participants to become accustomed to each other and the Facebook group features. Each week of the intervention, peer leaders will reach out to participants by posting on the online group forum, either text, images, or videos and sending direct messages to participants, attempting to promote COVID-19 vaccination through comforting and educational information/content of their choice. Every 2 weeks through the end of the study, participants in both conditions will be invited to email us to receive information about and receive related resources for COVID-19 vaccination, such as pamphlet on vaccination information. At the end of the 4-week intervention, participants will complete the final survey. Participants will be paid \$15 in Amazon gift cards for the baseline survey, \$20 in Amazon gift cards for the final survey, and \$15 in Amazon gift cards for providing proof of vaccination if applicable. Participants should expect about 4-6 weeks after completing respective tasks before receiving compensation. Participants will be contacted by phone and/or email to remind them to complete surveys as discussed above for the baseline survey.

All analyses will be conducted in R (version 4.1.2) We will assess the effect of the HOPE intervention on the primary outcome (whether a participant requested vaccine information during the study), and the secondary outcome (whether a participant got the vaccine during the study). We will adjust for race (dichotomized by Caucasian vs other), age (above vs. below 40), sex from birth, education (bachelor or below vs. grad school or above), and ethnicity (Latino vs. other).

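### Does the primary outcome leave it open whether a request made to a peer leader counts?

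*Combined protocol and SAP*

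**What the plan says.** Section 5 (Methods) gives the outcome in a parenthesis: "the primary outcome (whether a participant requested vaccine information during the study". The secondary outcome, vaccination, follows in the same sentence. The next paragraph names the models and defines weekly engagement, but it adds nothing on what a request is.

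The preceding paragraph of Methods describes how a request is made: "participants in both conditions will be invited to email us to receive information about and receive related resources for COVID-19 vaccination". The timing is "Every 2 weeks through the end of the study", and the intervention lasts 4 weeks.

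The two conditions differ in contact. Intervention participants sit in a Facebook group "with each participant assigned to have approximately 2-3 peer leaders". The leaders' work includes group posts and "sending direct messages to participants, attempting to promote COVID-19 vaccination through comforting and educational information/content of their choice". Controls have their own group and are "told they can interact with each other as they wish". On numbers, "Up to 30 peer leaders will be recruited using online advertisements as above". However, the sentence on group size in Methods, read literally, gives about 30 participants and about 6 peer leaders to every group, with 5 control and 5 intervention groups.

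The data-collection table in Section 8 has four rows: screener, baseline survey, 4-week survey and proof of vaccination. Peer leaders also submit "a tracking form by the weekly deadline that documents their efforts attempting to communicate with participants".

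**The concern.** The outcome phrase names no recipient or channel. An intervention participant who wants information can email the team or simply reply to a peer leader's direct message. If replies to peer leaders count, the intervention arm may gain events through a route that controls lack. If they do not count, requests that moved from email to a peer leader disappear from that arm. The two readings push the treatment difference in opposite directions.

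The Section 8 table has a row for proof of vaccination, which serves the secondary outcome, and none for requests. The tracking form concerns the leaders' own outreach. If the counting rule really were open, it could be settled after the data were seen, and that would matter for a primary outcome. The lack of a dated cut-off adds to the impression, because two-weekly invitations over 4 weeks can put the last one beside the final survey.

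**Working it through.** **1. Who has peer leaders?** Inputs: up to 30 leaders (Section 5, peer leader recruitment); about 6 per group, 5 control and 5 intervention groups (Section 5, Methods).

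- Intervention groups only: 5 x 6 = 30, which matches the stated maximum.
- All ten groups: 10 x 6 = 60, which does not.

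The arm descriptions and the count point to peer leaders in the intervention groups only. The group-size sentence reads otherwise and 30 is an upper limit, so this is a well-supported inference and not a stated fact.

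**2. Which requests does the plan describe?** Set side by side:

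- Email to the study team: participants are invited to ask, in both conditions, on a schedule.
- Peer leaders: the leaders reach out. No procedure is given for participants to request information from them.
- Facebook groups: participants in either arm could post a question. This is not described as a request either.

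Only the first is a procedure for requesting information, and it comes in the paragraph before the outcome is named.

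**3. Could the choice matter numerically?** The documents give no request rates and no intracluster correlation (ICC), so everything in this step is assumed.

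*Scenario A, diversion.* Any-route rates are 10% control and 20% intervention; s is the share of intervention requesters who ask only a peer leader. Email-only intervention rate = 0.20 x (1 - s).

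*Scenario B, extra route.* Emails are 10% in both arms; q is the share of intervention non-emailers who ask a peer leader. Any-route intervention rate = 0.10 + 0.90 x q.

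The chance of a significant benefit uses a noncentral t with 8 df, two-sided 0.05, 5 groups per arm and ICC 0.02. The design effect is 1 + (m - 1) x 0.02, which is 1.58 for m = 30 (the group size in Methods) and 1.22 for m = 12 (120 / 10, from the Section 4 maximum).

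| Case | Control vs intervention | Difference | m = 30 | m = 12 |
|---|---|---|---|---|
| A, any route | 10% vs 20% | +10 | 40% | 24% |
| A, email, s = 25% | 10% vs 15% | +5 | 15% | 10% |
| A, email, s = 50% | 10% vs 10% | 0 | 2.5% | 2.5% |
| A, email, s = 75% | 10% vs 5% | -5 | 0.1% | 0.3% |
| B, any route, q = 10% | 10% vs 19% | +9 | 35% | 20% |
| B, any route, q = 20% | 10% vs 28% | +18 | 81% | 54% |

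Worked line (A, any route, m = 30): variance = (0.10 x 0.90 + 0.20 x 0.80) x 1.58 / 150 = 0.00263, standard error 0.0513, noncentrality 0.10 / 0.0513 = 1.95, chance 40%. With ICC 0 it is 58%; with ICC 0.05, 28%.

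At s = 0 or q = 0 the two readings agree. The table shows that the choice could matter, but nothing in the documents says where s or q would fall. It also holds control requests by other routes fixed.

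**4. What would a written rule change?** Stating that only emails count would give the email rows of scenario A, which is what an analyst following the plan gets already. Any diversion to peer leaders would remain.

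**The case for a change.** The strongest case for a change is that the plan defines engagement in detail but leaves its primary outcome to a short phrase, that the ambiguity falls unevenly on the arms, and that one sentence would close it before any data are seen. Email-only is not neutral either, since it can miss intervention participants who asked a peer leader instead.

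Part of this stands. The text never expressly ties the outcome to the email invitation, and no source in the Section 8 table is described as recording requests. A clarifying sentence would be harmless, and the group-size wording on peer leaders should be reconciled with the total of 30.

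The rest is weaker:

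- The contents of the 4-week survey are not shown, so it cannot be said that no listed source records requests. Weekly engagement, which the plan does define, has no row in the table either, so a missing row is poor evidence that a measure is unplanned. Emails to the team leave their own record.
- The ambiguity is not confined to one arm. Control participants can also post questions in their group.
- The window is described, though undated: during the study, with a 4-week intervention. A late invitation reaches both conditions alike, so no bias between arms has been shown.

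**Conclusion.** The concern does not call for a change. This is missing detail that analysts would fill sensibly: the event is an email to the study team asking for vaccine information, the only request procedure described and one offered equally to both conditions. Writing that down would confirm the natural reading without altering the analysis or removing any diversion of requests to peer leaders.

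No size can be given from the documents. The email-only differences of +5 to -5 points, and the any-route gains of 9 and 18 points where emails are equal, rest wholly on assumed request rates, assumed shares asking only a peer leader and an assumed ICC. If nobody asks only a peer leader, the readings coincide. The conclusion assumes that the email invitation is the intended event; the order of the Methods text supports this, but the plan does not say so outright.
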